#### 11.3.3 Definition of SUSAR

A Suspected Unexpected serious Adverse Reaction (SUSAR) is a serious adverse reaction for which the nature and severity is not consistent with the information set out in the reference Safety Information (see IB).

#### 11.3.4 Recording and follow-up of AE and/or SAE

### AE and SAE recording

When an AE/SAE occurs, either spontaneously revealed by the patient or observed by the Investigator, and whether believed by the Investigator to be related or unrelated to the study drug, it is the responsibility of the Investigator to review all documentation (e.g., hospital progress notes, laboratory, and diagnostics reports) related to the event.

- The Investigator will record all relevant AE/SAE information on the AE CRFs/worksheets at each examination.
- It is not acceptable for the Investigator to send photocopies of the participant's medical records to the Sponsor in lieu of completion of the AE eCRF page.

- There may be instances when copies of medical records for certain cases are requested by the Sponsor. In this case, all participant identifiers, with the exception of the participant number, will be blinded on the copies of the medical records before submission to the Sponsor.
- The investigator will attempt to establish a diagnosis of the event based on signs, symptoms, and/or other clinical information. In such cases, the diagnosis (not the individual signs/symptoms) will be documented as the AE/SAE.
- As far as possible, each AE/SAE is described by: duration (start and end dates), event verbatim, solicited/unsolicited, frequency (relationship to the study treatment), intensity grade, seriousness, action taken and outcome.

#### Assessment of intensity

The investigator will make an assessment of intensity for each AE and SAE (and other reportable safety event) by recording the grade according to the Table for Grading the Severity of Adult and Pediatric Adverse Events (NIH DAIDS version 2.1, 2017). Any AE which changes DAIDS grade over the course of a given episode will have each change of grade recorded on the AE CRFs/worksheets.

- Grade 1 Mild event: Mild symptoms causing no or minimal interference with usual social and functional activities with intervention not indicated.
- Grade 2 Moderate event: Moderate symptoms causing greater than minimal interference with usual social and functional activities with intervention indicated.
- Grade 3 Severe event: Severe symptoms causing inability to perform usual social and functional activities with intervention or hospitalization indicated.
- Grade 4 Potentially life-threatening event: Potentially life-threatening symptoms causing inability to perform basic self-care functions with intervention indicated to prevent permanent impairment, persistent disability, or death.
- Grade 5 Death: Deaths related to an AE.

An event is defined as "serious" when it meets at least 1 of the predefined outcomes as described in the definition of an SAE, NOT when it is rated as severe.

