## 3.2 Endpoints

#### 3.2.1 Primary endpoints

- Number of Adverse events (AEs), serious AEs (SAEs) (Common Terminology Criteria Adverse Events [CTC-AE]) from ICF signature to D29, including target knee pain and tenderness, erythema, swelling, local pain at injection site.
- Vital signs from D-7 to D8, ECG from D-7 to D1: Mean change, number of Potentially Clinically Significant Abnormality (PCSA), Percentage of participants with PCSA
- Laboratory changes (Red Blood Cells (RBC), White Blood Cells (WBC), Hemoglobin (Hb), platelets, alanine transaminase (ALT), aspartate transaminase (AST), glycemia, amylasemia, creatinin clearance) from D-7 to D8: Mean changes number of PCSA, Percentage of participants with PCSA.

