## AEs

All AEs will be coded by system organ class (SOC) and preferred term (PT) using the Medical Dictionary for Regulatory Activities (MedDRA). Clinical judgment should be used to determine the severity of AEs as described in Section 11.3.4.

TEAEs with onset occurring within 7 days (onset date – date of dose +  $1 \le 7$ ) after study drug administration will be listed and included in the summary tables. TEAEs will be summarized by SOC and PT. The following summary tables will be included in the report: summary of TEAEs and drug-related AEs, relationship of AEs to study drug (related vs not-related), severity of AEs and related AEs. AEs leading to study drug discontinuation and SAEs will be listed. Data listings will be provided for all AEs including PTE, TEAEs, AEs leading to study drug discontinuation, and SAEs.

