#### 12.2.1 Definitions

Adverse events will be classified in one of three categories:

- pre-treament: events that certainly started during screening
- post-treatment: events that certainly started after the treatment period
- treatment-emergent (TEAE): all other events

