#### 12.2.2 Overview of TEAEs

This table will also show the number of AEs, as depicted below.

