**Table TTT. Overview of TEAEs** 

	Placebo		4P004									
	(pooled)										(pooled)	
	(N=XX)		(N=XX)		(N=XX)		(N=XX)		(N=XX)		(N=XX)	
	Subjects	# 	Subjects	#1								
Any TEAE	XX (X.X%)	XX	XX (X.X%)	XX								
AESI	XX (X.X%)	XX	XX (X.X%)	XX								
SAEs	XX (X.X%)	XX	XX (X.X%)	XX								
by Toxicity Grade												
1 Mild	XX (X.X%)	XX	XX (X.X%)	XX								
2 Moderate	XX (X.X%)	XX	XX (X.X%)	XX								
by Relationship to Study Drug												
Not Related	XX (X.X%)	XX	XX (X.X%)	XX								
Unlikely	XX (X.X%)	XX	XX (X.X%)	XX								
()	XX (X.X%)	XX	XX (X.X%)	XX								
by Outcome												
Recovered	XX (X.X%)	XX	XX (X.X%)	XX								
Recovering	XX (X.X%)	XX	XX (X.X%)	XX								
()	XX (X.X%)	XX	XX (X.X%)	XX								

<sup>1 Numbers of adverse events

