### 12.2.3 All TEAEs

Table TTT. TEAEs by SOC and PT

SOC	Placebo	4P004	4P004	4P004	4P004	4P004
PT	(pooled)					(pooled)
	(N=XX)	(N=XX)	(N=XX)	(N=XX)	(N=XX)	(N=XX)
Any TEAE	XX (XX.X%)					
SOC term	XX (XX.X%)					
PT term	XX (XX.X%)					
()	XX (XX.X%)					
SOC term	XX (XX.X%)					
PT term	XX (XX.X%)					
()	XX (XX.X%)					

Table TTT. TEAEs by SOC, PT and Toxicity Grade

SOC	Toxicity	Placebo	4P004	4P004	4P004	4P004	4P004
PT	Grade	(pooled)					(pooled)
		(N=XX)	(N=XX)	(N=XX)	(N=XX)	(N=XX)	(N=XX)
Any TEAE	1 Mild	XX (XX.X%)					
	2 Moderate	XX (XX.X%)					
	()	XX (XX.X%)					
SOC term	1 Mild	XX (XX.X%)					
	2 Moderate	XX (XX.X%)					
	()	XX (XX.X%)					
PT term	1 Mild	XX (XX.X%)					
	2 Moderate	XX (XX.X%)					
	()	XX (XX.X%)					
()							
SOC term	1 Mild	XX (XX.X%)					
	2 Moderate	XX (XX.X%)					
	()	XX (XX.X%)					
PT term	1 Mild	XX (XX.X%)					
	2 Moderate	XX (XX.X%)					
	()	XX (XX.X%)					
()		•	•	•	•	•	

With the same template, the TEAEs will be presented by Relationship to study drug, grouped as:

- Not related: No/Unlikely
- Related: Possible, Probable, Definite

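### Treatment-emergent status rests on AE start alone, so an AE open at injection whose grade then rises is missing from every TEAE and AESI summary table

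*Protocol*

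**What the plan says.** **Recording.** Protocol 11.3.4 (Assessment of intensity) requires: "Any AE which changes DAIDS grade over the course of a given episode will have each change of grade recorded on the AE CRFs/worksheets". AEs are collected from consent (Protocol 8.2.1), and screening takes place 4 to 14 days before dosing, so an AE can already be open at injection.

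**Endpoint.** The first primary endpoint in Protocol 3.2.1 opens with "Number of Adverse events (AEs), serious AEs (SAEs" and runs from consent to D29.

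**Classification.** SAP 12.2.1 has three classes. Pre-treatment means "events that certainly started during screening". Post-treatment means a certain start after the treatment period. The remainder is "treatment-emergent (TEAE): all other events". Protocol 10.1.4 (AEs) tabulates "TEAEs with onset occurring within 7 days" of dosing. SAP 9.4 sets the treatment period as injection to 7 days after the injection date.

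**Tabulation.** On the overview table, SAP 12.2.2 says "This table will also show the number of AEs, as depicted below", and the footnote gives the unit as "Numbers of adverse events". The severity shell in SAP 12.2.3, "Table TTT. TEAEs by SOC, PT and Toxicity Grade", has a grade column with no mention of a maximum. The injection-site shell in SAP 12.2.5 does specify maximum grade, in line with Protocol 10.1.4 (Local tolerability).

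**The concern.** A TEAE table is meant to show what appeared or got worse after dosing. Here only appearance counts. The trial collects the information that would show worsening, grade change by grade change, but the classification rule does not use it.

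What is at stake is the between-dose safety summary in a trial whose primary purpose is tolerability. The AESI tables show the problem most clearly. Two of the AESI categories, gastro-intestinal disorder and injection-site reaction, depend on the event being severe. A gastro-intestinal AE that was mild in screening and severe after injection would become an AESI because of what happened after dosing. Its start would still make it pre-treatment, so it would be left out of the treatment-emergent AESI tables and of the treatment-emergent AESI listing.

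**Working it through.** The documents state no figure on this point, so there is none to reproduce. The check is a matter of following one event through the rules.

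**Test case (hypothetical).** An AE starts during screening at Grade 1, is still open at injection, and reaches Grade 2 on D2.

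1. *Recording.* Protocol 11.3.4 speaks of one AE whose grade changes within one episode. The same section describes each AE by start and end dates and an intensity grade. The plain reading is one AE, one start date, with the change to Grade 2 noted.
2. *Classification.* The start is certainly in screening, so SAP 12.2.1 makes it pre-treatment. The default to TEAE helps only when the start date is uncertain. It does nothing for a known start followed by worsening.
3. *Protocol rule.* Onset precedes dosing, so the event is not a TEAE under Protocol 10.1.4 either.
4. *Output.* In the list in SAP 17, the event is absent from Tables 3.1, 3.1.1, 3.1.2 and 3.1.3. If it is an AESI, it is also absent from Tables 3.2 and 3.2.1 and Listing 3.2.2. It remains in Listing 16.2.9 and, if serious, in Listing 3.4.

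**The same case under the other recording route.** If the investigator reports the worsening as a new AE with a start after injection, it is a TEAE. Protocol 11.3.1 permits this, because an increase in intensity of an existing condition meets the AE definition. The same clinical course is thus in or out of the tables according to how it was written down.

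**Weight of one such participant** (planned arm sizes, 6 active and 2 placebo in each of 4 cohorts):

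| Column | N | One participant |
|---|---|---|
| One dose level | 6 | 1/6 = 16.7 points |
| Pooled placebo | 4 × 2 = 8 | 1/8 = 12.5 points |
| Pooled 4P-004 | 4 × 6 = 24 | 1/24 = 4.2 points |

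These show what a single case would do to a row. They do not estimate how many cases there are.

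**Why the by-grade tables need a word as well.** Suppose 5 participants with nausea each passed through Grades 1 and 2 (an assumption; Protocol 2.3 gives 5 participants with nausea in cohort 3 but no grades). Without a maximum rule each could be counted in two rows:

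| Assumed N | Sum of the two rows, 2 × 5/N | Under a maximum rule, 5/N |
|---|---|---|
| 6 | 166.7% | 83.3% |
| 8 | 125.0% | 62.5% |
| 9 | 111.1% | 55.6% |

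The cohort 3 figures come from a blinded review that mixes arms, so none of these values of N is established for nausea.

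**The case against.** The strongest reply is that little is actually lost. The primary endpoint runs from consent, so a screening AE belongs to it whatever its class. All AEs are listed, the DSMB reviews every reported AESI, and no significance tests are made on safety data. The listed dose-limiting toxicities are specific events and thresholds, not TEAE percentages. A flare of the knee pain that participants bring into the trial is a worsening of a pre-existing condition. It can be reported as a new AE after injection, so it is not caught by this gap.

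All of that stands, and it confines the point to AEs opened during screening and kept as one entry. It does not answer the point for those AEs. Their tabulation depends on a reporting habit that neither document fixes, and a reader of the summary tables would not know that anything was missing.

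Two stronger readings are tempting. A reader might infer that every grade change adds to the number of AEs, so that event counts double or triple. The documents do not support this: the SAP counts adverse events, not data entries, and Protocol 11.3.4 describes changes within one AE. If changes stay inside that AE, the count is unaffected. Multiplication would need each change to be counted separately and an assumed share of episodes to change grade, and neither is stated.

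A reader might also infer that the primary count is wrong however the data are stored. That does not follow. For one episode, inflation and missed worsening are alternatives. An entry kept whole is not counted twice, and a worsening entered separately with a post-injection start is not missed.

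**Conclusion.** The point holds as a gap in the TEAE definition. Applied as written, SAP 12.2.1 puts an AE that worsened after injection among the pre-treatment events and so leaves it out of all TEAE and AESI summaries. This rests on two assumptions: that a grade change is kept within the same AE, which is how Protocol 11.3.4 reads, and that the investigator does not open a new AE for the worsening. The eCRF layout is not in the documents.

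The number of participants affected cannot be determined from the documents and may be zero. One case would move a dose-level row by 16.7 points at N = 6. The event stays in the listings, so the loss is from the summaries and not from the trial record.

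The missing statements on one event per episode and on maximum grade are secondary. Most analysts would fill them in sensibly. The difference between the TEAE shells and the injection-site shell is nevertheless real and worth removing.

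**What to change.** In SAP 12.2.1, add that an AE which started before injection and whose DAIDS grade increased between injection and the end of the treatment period (SAP 9.4) is also treatment-emergent. Use the recorded grade changes and their dates.

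As accompanying clarifications in SAP 12.2:

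- State that one episode counts as one event, whatever the number of grade changes.
- In the overview by grade, the TEAE by-grade table and the AESI by-grade table, count each participant once, at the maximum post-injection grade within the treatment period. In the SOC and PT rows, apply this within each term. Label the column as in SAP 12.2.5.

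Before programming, check how the eCRF stores a grade change and its date, so that the derivation matches the data.

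The cost is a few sentences in the SAP and one derivation step before database lock. No new data are needed, because the protocol already requires each grade change to be recorded.

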### Assessment of causality

The relationship of each AE to study intervention will be assessed using the following categories:

- Related: An AE that follows a reasonable temporal sequence from administration of a drug (including the course after withdrawal of the drug), or for which possible involvement of the drug cannot be ruled out, although factors other than the drug, such as underlying diseases, complications, concomitant drugs and concurrent treatments, may also be responsible.
- Not Related: An AE that does not follow a reasonable temporal sequence from administration of a drug and/or that can reasonably be explained by other factors, such as underlying diseases, complications, concomitant drugs and concurrent treatments.

Category	Criteria	Final reporting of relationship to study drug (interpretation used for regulatory reporting purpose)
Definitely (must have all the mentioned criteria)	
 
Follows a reasonable temporal sequence from administration of the drug
 
Cannot be reasonably explained by the known characteristics of the patient's clinical state, environment or toxic factors, or other modes of therapy administered to the patient
 
Disappears or decreases on cessation or reduction in dose and recurs with re-exposure to drug (if rechallenge occurs)
 
Follows a known pattern of response to the drug
 
	
Probable (must have the first three)	
 
Follows a reasonable temporal sequence from administration of the drug
 
Cannot be reasonably explained by the known characteristics of the patient's clinical state, environment or toxic factors, or other modes of therapy administered to the patient
 
Disappears or decreases on cessation or reduction in dose
 
Follows a known patter of response to the drug
 
Reappears on re-challenge
 
	Related
Possible (must have the first two)	
 
Follows a reasonable temporal sequence from administration of the drug
 
May have been produced by the patient's clinical state, environment or toxic factors, or other modes of therapy administered to the patient
 
Follows a known pattern of response to the suspected drug
 
	
Unlikely (must have the first two)	
 
Does not follow a reasonable temporal sequence from administration of the drug
 
May readily have been produced by the patient's clinical state, environment or toxic factors, or other modes of therapy administered to the patient
 
Does not reappear or worsen when the drug is readministered
 
	Not related
Unrelated	
 
Is clearly and incontrovertibly due to extraneous causes (disease, environment, etc.)
 
Do not meet the criteria for drug relationship listed under Unlikely, Possible, Probable or Definitely
 
	

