## Stopping rules

The study will be immediately suspended, and no additional IMP administered pending review and discussion of all appropriate study data by the DSMB if 1 or more participants develop any of the following adverse events deemed to be possibly, probably, or definitely related to the IMP by the Investigator and/or Medical Monitor, based upon close temporal relationship or other factors:

- Severe local reaction within 7 days after injection
- Clinical manifestations of hypoglycemia
- Severe gastro-intestinal adverse event
- Potentially clinically significant ECG abnormalities.
- Any serious adverse event considered reasonably related to the IMP (SAR) by the Principal Investigator.

The study will not be restarted until all parties have agreed to the course of action to be taken and the EC has been notified.

Dose limiting toxicity (DLT) describes side effects of a drug that are serious enough to prevent an increase in dose or level of that treatment.

When more than 1 DLT occurs in a dosing cohort, dose escalation must be stopped and this dose level will be identified as the non-tolerated dose.

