## 10.2 Sample size determination

The sample size for this study of 8 participants in each cohort (6 active : 2 placebo) is considered to be sufficient for evaluation of safety, tolerability, and PK of each cohort. The sample size was not based on statistical power considerations.

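### Protocol 11.3.4: the prose definition of Not Related overlaps Related and contradicts the five-level causality table, and no sentence says which governs

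*Protocol*

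**What the plan says.** Protocol 11.3.4 (Assessment of causality) first offers two prose categories as the ones to be used for rating each event.

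- *Related*: "An AE that follows a reasonable temporal sequence from administration of a drug (including the course after withdrawal of the drug", or an event where involvement of the drug cannot be ruled out. The definition accepts that underlying disease or concomitant drugs may share responsibility.
- *Not Related* is worded as "An AE that does not follow a reasonable temporal sequence from administration of a drug and/or that can reasonably be explained by other factors". The factors listed are the same ones.

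A five-level table follows, with a column for the final reported relationship.

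- *Definitely*, *Probable* and *Possible* are reported as Related. *Possible* requires reasonable timing and a second criterion: "May have been produced by the patient's clinical state, environment or toxic factors, or other modes of therapy administered to the patient".
- *Unlikely* and *Unrelated* are reported as Not related. The first mandatory criterion for *Unlikely* is "Does not follow a reasonable temporal sequence from administration of the drug". *Unrelated* needs a clear and incontrovertible extraneous cause, or that no other row is met.

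Elsewhere, the suspension rule in protocol 4.6.1 covers listed events "deemed to be possibly, probably, or definitely related to the IMP by the Investigator and/or Medical Monitor". The DLT text in the same section includes any related SAE without naming a scale. Protocol 10.1.4 plans tables split into related and not related. SAP 12.2.3 groups the levels as "Related: Possible, Probable, Definite", against No and Unlikely for not related. The overview table in SAP 12.2.2 lists Not Related and Unlikely as separate rows.

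**The concern.** The two prose categories should exclude each other, and they do not. The problem is the and/or in *Not Related*: a reasonable alternative explanation is enough by itself, even when the timing fits the drug. *Related* is met by that same timing.

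Events of this kind can be expected here. Every participant has osteoarthritis of the injected knee, so a worsening of target-knee pain soon after injection can have both plausible timing and a disease explanation. Protocol 6.5 allows NSAIDs, tramadol and opioids, so nausea in a user may have a concomitant-drug explanation. Protocol 2.3 already reports nausea in 5 and vomiting in 4 participants of cohort 3.

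The naming makes the prose easier to reach. The lowest level is *Unrelated* in the protocol table, *No* in SAP 12.2.3 and *Not Related* in the SAP 12.2.2 overview. The last is the label that the prose defines. The documents do not show the eCRF. If it carries that label, a rater who looks it up finds the and/or definition, and the event then enters the not-related group in the SAP tables.

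**Working it through.** The plan states no figure on this point, and none could come from the sample size: "The sample size was not based on statistical power considerations". The check is logical, followed by simple division.

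**Step 1. Symbols.** T: timing is reasonable. R: involvement of the drug cannot be ruled out. O: other factors can reasonably explain the event, short of being its incontrovertible cause.

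- Prose Related = T or R.
- Prose Not Related = (not T) or O.
- Five-level table: mandatory criteria only. I assume that an event other factors can reasonably explain also meets the table's criterion that they may have produced it.

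**Step 2. All eight combinations.**

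| T | R | O | Prose Related | Prose Not Related | Five-level table |
|---|---|---|---|---|---|
| yes | yes | yes | yes | yes | Possible, so Related |
| yes | no | yes | yes | yes | Possible, so Related |
| yes | yes | no | yes | no | Probable or Definitely if dechallenge is met; otherwise Unrelated by default |
| yes | no | no | yes | no | as above |
| no | yes | yes | yes | yes | Unlikely, so Not related |
| no | yes | no | yes | yes | Unrelated by default |
| no | no | yes | no | yes | Unlikely, so Not related |
| no | no | no | no | yes | Unrelated by default |

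Four of the eight meet both prose definitions. The two that matter here are the first two rows: reasonable timing with another explanation. For both, the table gives one answer, Related, while prose *Not Related* is also satisfied.

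**Step 3. Would changing and/or to and be enough?** Not Related then becomes (not T) and O. The first two rows become Related only. But T no, R yes, O yes still meets both definitions, and T no, R no, O no now meets neither. The single word does not give one answer per event.

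**Step 4. Size of one reclassified participant**, at the planned 6 active and 2 placebo in each of 4 cohorts:

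- one dose group: 1/6 = 16.7 percentage points;
- pooled active: 4 × 6 = 24, and 1/24 = 4.2 points;
- pooled placebo: 4 × 2 = 8, and 1/8 = 12.5 points.

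SAP 9.3 adds a ninth participant to cohort 3 on the same treatment as an underdosed one. Pooled active may therefore be 25 (1/25 = 4.0 points) or pooled placebo 9 (1/9 = 11.1 points). If an underdosed active participant is kept in the planned arm, that arm has 7 (1/7 = 14.3 points).

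**The case against.** The strongest reply is that the section settles the matter itself. The table has an explicit final-reporting column, and it returns Related for the disputed event. The suspension rule uses the table's terms, and SAP 12.2.3 builds its grouping from them. The SAP overview also lists graded levels, which suggests that these are what sites record. SUSAR classification is a regulatory use that the column names, and protocol 8.2.4 gives that assessment to the sponsor. A reader might infer from the prose overlap that the plan leaves the count open, so that the same event may equally be counted or not. The documents do not support that: where a scale is named, it points to Related.

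The consequences are also limited.

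- The primary endpoint in protocol 3.2.1 is the number of AEs and SAEs, not of related ones. SAP 12.2.3 tabulates all TEAEs regardless of relationship, beside pooled placebo.
- All SAEs are reported whatever their relationship (protocol 11.3.5), and the DSMB reviews all AESIs (8.2.6).
- The four specific DLTs in protocol 4.6.1 carry no relatedness condition. The suspension rule covers only its listed events, and the medical monitor may also judge relatedness.
- Protocol 11.3.1 removes expected fluctuations of existing disease that do not worsen, so part of the osteoarthritis background is never rated.
- The 16.7 points is simply one participant in six and would fit any miscoded yes/no item.

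All of this stands, and it limits the size of the point. It does not remove the contradiction. A grouping rule sorts ratings once they are made; it does not control which definition the rater used. The prose is introduced as the scale for rating, no sentence subordinates it, and one SAP table carries its label.

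**Conclusion.** The contradiction is real and confined to wording. For an event with reasonable timing and another reasonable explanation, prose *Not Related* conflicts both with prose *Related* and with the *Possible* row. The remaining risk is that a site rates from the prose and records as not related what the table counts as related.

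That would affect the related-event tables of protocol 10.1.4 and SAP 12.2.3. It would reach the suspension rule, or the related-SAE limb of the DLT text, only for the event types named there. A reader might go further and infer that dose-limiting toxicity, or the tolerated dose, is generally undetermined. The text does not support that, since the specific DLTs do not depend on relatedness and a dose is labelled non-tolerated only on more than one DLT.

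The shifts in step 4 are per reclassified participant. They assume the planned arm sizes, or the SAP 9.3 variants shown. They are not estimates of how much the results will move, because the documents give no rate of ambiguous events and do not show the eCRF categories.

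**What to change.** Reconcile the passages in three edits.

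1. In protocol 11.3.4, delete the two prose definitions or rewrite them to match the table.
2. Add one sentence stating that the five-level table governs the eCRF rating, the related and not-related tables, and every rule that refers to relatedness. The lists of events in the suspension and DLT rules are untouched.
3. Use one name for the lowest level in the protocol table, SAP 12.2.2 and SAP 12.2.3.

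Making the table govern settles the case described here. It leaves one case to check during the edit: an event with reasonable timing, no other explanation and the dechallenge criterion unmet or not assessable fits no row except *Unrelated* by default.

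SAP 5.1 describes enrolment in the past tense, so ratings already exist and new wording alone will not reach them. Before the data review meeting in SAP 6.2, list, blind to treatment, the events with plausible timing recorded at the lowest level, and query the site on which definition was applied.

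The cost is a short protocol and SAP correction, a site reminder and some queries. A few more events may be reported as related. No sample size, alpha or power figure changes.
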